#### Laboratory outcomes

**AIM6: Immune cell sub-populations and responsiveness over time,** measured by immunophenotyping, cell activation and cytokine production following in-vitro stimulation with unrelated pathogens, Toll-like receptor (TLR) agonist or molecules derived from pathogens (as described in), in bloods collected at 6 months, 9 months, and 24 months of age.

**AIM7: Transcriptional responses and epigenetic imprinting in immune cells** (e.g. monocytes) in bloods collected at 6 months, 9 months, and 24 months of age, identifying functional pathways that are impacted by MMR and that might contribute to the clinical non-specific effects observed.

**AIM8: Vaccine responses and memory cells** in bloods collected at 6 months, 9 months, and 24 months of age.

**AIM9: Influence of interventions, children, maternal and environmental factors on laboratory outcomes:** Factorial and multivariate analyses will assess the impact of interventions (early MMR, non-concomitant MMR), host factors (e.g. sex, ethnicity), exposure (e.g. day-care, siblings, pets, smoking), underlying immunity (e.g. previous infections), and familial history (e.g. allergy) on laboratory outcomes defined above.

### 5.3 Other Outcomes of Interest

Exploratory outcome measures may be examined, pending additional funding. These may include measures of metabolomic and lipidomic profile, in particular the quantification of glycoprotein acetyls, a marker of cumulative acute and chronic inflammation, commonly used as a surrogate of infection burden.

### 5.4 Safety Outcomes

**AIM10: Vaccine safety:** occurrence and severity of local and systemic adverse events, as well as any serious adverse events, by systemic organ class, preferred term, severity using toxicity grading scale, and relationship to the intervention from day 0 to day 42 post MMR.

## 6. STUDY DESIGN

### 6.1 General study design and justification of design

#### 6.1.1 Study design and framework

This is a phase IV, single-center, open-label, randomised controlled trial with a factorial design, aiming to demonstrate the superiority of a modified vaccination schedule, compared with the current Swiss vaccination schedule for MMR.

#### 6.1.2 Participants

500 children healthy children followed-up in Geneva, including a subset of 100 children with blood tests (see section 7 *Study population*, and section 11.2 *Sample size*).

#### 6.1.3 Intervention and comparator

This trial will compare the current Swiss vaccine administration schedule (control group) with a modified schedule (intervention groups), designed to maximise the beneficial non-specific effects of MMR (Fig 8 and Table 1). The intervention will be the same (0.5 ml of the MMR vaccine injected intramuscularly), the only change is the timing of administration. **The factorial design will enable to measure the benefit of the intervention on each of the two doses of MMR separately or in combination** (Table 2). The intervention on the administration of the first dose of MMR is to give it at 6 months of age instead of 9 months of age; the intervention on the administration of the second dose of MMR is to give it 1 month after the 1-year non-live vaccines instead of concomitantly to them.

Whereas this will be a classic 2-arm trial with regard to the first intervention (early 1st MMR dose) and the primary outcome (number of respiratory infections between 6 and 9 months), the second phase will be a factorial trial, crossing the first component (early 1st MMR dose) with the second component (separated 2nd MMR dose). This design will allow a separate assessment of the impact of the 2 components on secondary outcomes measured until 24 months of age. The utility of the separate assessment of the 2 components is both scientific (better understanding of the mode of action of the modified schedule) and pragmatic (the modified schedule may imply that an additional medical visits is required (i.e. at 13 months of age to administer the 2nd MMR not concomitantly to the other 12-months vaccines) and if one was unnecessary (i.e. if the first component has the greatest impact, the additional impact from the second component is negligible) the intervention with only one of the two components would be more practical and cheaper).

	Current schedule	Modified schedule	Comment – Rational for change
1 st DTP and PCV	2 m	2 m	No change
2 nd DTP and PCV	4 m	4 m	No change
1 st MMR	9 m	6 m	As soon as possible after 2 nd DTP-PCV (both non-live vaccines)
3 rd DTP and PCV	11-13 m	11-12 m	Before and not concomitantly to 2 nd MMR
2 nd MMR	11-13 m	13 m	Given on its own, after 3 rd DTP-PCV (→ most recent vaccine live)

Table 1: Current Swiss vaccine administration schedule compared to the proposed modified schedule, with rational for change. m: months of age; PCV: pneumococcal conjugate vaccine (a non-live vaccine). See also Fig 8.

		Stage B: comparison for the timing of the 2 nd MMR		
		2 nd MMR 1m after the 12y DTP-PCV (Modified)	2 nd MMR concomitant with the 12y DTP-PCV (Current)	
Stage A: comparison for the timing of the 1 st MMR	1 st MMR at 6m (Modified)	Group M.M. , n=125 (including 25 in Part 2)	Group M.C. , n=125 (including 25 in Part 2)	N=250 (including 50 in Part 2)
	1 st MMR at 9m (Current)	Group C.M. , n=125 (including 25 in Part 2)	Group C.C. , n=125 (including 25 in Part 2)	N=250 (including 50 in Part 2)
		N=250 (including 50 in Part 2)	N=250 (including 50 in Part 2)	

Table 2. Participant allocation in 4 groups; see also Table 3. C: current MMR schedule; DTP: diphtheria-tetanus-pertussis vaccine; m: month; M: Modified MMR schedule; PCV: pneumococcal conjugate vaccine.

[figure not shown]

Fig 8: Current Swiss administration schedule and Study flowchart.

#### 6.1.4 Duration of volunteers' participation

Participants will be followed-up for 18 months after randomisation, namely from 6 months to 24 months of age.

#### 6.1.5 Study procedure and measurement

A minimum of three visits are planned, at 6 months of age (for inclusion, randomisation, ± vaccination, ± blood collection), 9 months of age (for ± vaccination, ± blood collection), and 24 months of age (for ± blood collection). Providing sufficient funding, an additional visit at 12-13 months of age (for vaccination) is planned at the Platform of clinical research in Paediatrics; if funding is insufficient, tasks will be delegated to the treating paediatrician who would do it during their routine follow-up visit. Parents will be asked to complete questionnaires once every 2 weeks for the first 3 months, then once every month.

### 6.2 Methods of minimising bias

#### 6.2.1 Randomisation

Consent to blood tests at 6, 9 and 24 months of age will be sought, and will determine whether a child participates in Part 1 only, or both Part 1 and Part 2. Participant will be randomly allocated at inclusion to four equal groups, using a web-based randomisation procedure, stratified by consent to blood tests (yes/no), in randomly permuted blocks of variable length (4 or 8), enabling to prevent predictability of intervention assignments. The randomisation lists will be generated prior to the initiation of the study by someone not involved in the study analysis and will be integrated into REDCap.

#### 6.2.2 Blinding procedures

Investigators involved in data cleaning and analyses will be blinded to allocation in order to avoid the introduction of bias between study arms, until statistical analyses have been completed.

#### 6.2.3 Other methods of minimising bias

Validated questionnaire will be used when available (see section 9.2)

### 6.3 Unblinding Procedures (Code break)

Not applicable.

### 6.4 Risk mitigation of the trial design

**Variability in infectious risk:** Individual risk of infection depends on host (predisposition) and environmental (exposure) factors. Randomisation should ensure that risk factors are equally distributed between the two groups. The risk of those factors influencing the outcomes is also addressed by adjusting the analyses by the presence of comorbidities (host predisposition), siblings and day-care attendance (environmental exposure).

**Recruitment:** Recruitment will be through a network of private paediatricians highly motivated in contributing to clinical research. Pamphlets will be distributed in maternity services and paediatricians' offices; infants will be recruited during the first few months of age and parents will have opportunity to ask questions before the randomisation visit at 6 months of age. With over 5000 live births per year in Geneva, a minimum acceptance rate of 5% for Part 1 (questionnaires only) and of 1% for blood testing will enable recruitment to be completed in 18 months.

**Study burden / acceptance of the study:** The online questionnaire is being designed in partnership with parents in order to make it as user-friendly as possible. It will be completed every 2 weeks by participants' parents on a smartphone, computer or tablet following a participant-specific link sent by text or email, and will take less than 10 minutes to complete. The questionnaire includes many fields per participant but, thanks to branching algorithms, only items relevant to each participant will be displayed (based on the answers to previous questions). This design reduces redundancy and reduces the risk of missing or duplicate data.

**Accuracy of parent-reported data:** The questionnaire uses pre-filled fields, drop-down menus, and other measures to reduce the time taken for completion, and to increase the accuracy of the data. The data will be reviewed with the treating paediatrician, and the parents during the clinic visit, to retrieve any missing information. The child's medical records will also be checked. Clinical assessment will take place during the study visit to confirm some of the outcomes (e.g. presence of eczema using validated scores).

**Blood collection in infants:** Blood volume collected will be kept to the strict minimal and within the range proven to be safe in children. The study visits will be held at the Platform of Clinical Research in Paediatric, Gynaecology & Obstetrics, and the blood collection will be done in collaboration with research nurses who are experienced in collecting blood from infants. The use of analgesia cream, correct positioning and distraction of the child will minimise pain. The minimum of a 3-months gap between the visits and blood collection will increase acceptability.

**Extensive laboratory analysis:** The teams of [name] (Center of Vaccinology, Geneva), and [name] (Murdoch Children's Research Institute, Melbourne) have long experience in performing all the experiments described, including the in-vitro assays on whole blood and downstream sample analysis, as well as whole genome transcriptomic analysis, in infectious disease and vaccine studies. We will also have access to the support of a bioinformatician who is currently working in the laboratory of [name] and supporting in transcriptomic and epigenetic analyses. The genomic platform of the University of Geneva have internationally recognised expertise for such experiments (<https://ige3.genomics.unige.ch/>).

## 7. STUDY POPULATION

### 7.1 Eligibility criteria

#### 7.1.1 Inclusion criteria

Participants fulfilling all of the following [inclusion](#) criteria are eligible for the study:

- 1) Informed Consent as documented by signature
- 2) 6-month-old children
- 3) In overall good health, without any clinically significant concomitant disease states (e.g., renal failure, hepatic dysfunction, cardiovascular disease, etc.) and no clinically significant abnormal finding on history and/or physical examination
- 4) Fully immunised for age according to the Swiss vaccination schedule
  - a) with at least 2 doses of DTP-containing vaccine
  - b) the last dose of vaccine received at least 2 weeks prior to enrolment

#### 7.1.2 Exclusion criteria

The presence of any one of the following [exclusion](#) criteria will lead to exclusion of the participant:

- 1) Contra-indications to MMR, including
  - a) immunosuppression (i.e. proven, suspected, or planned)
  - b) allergy to a component of the vaccine
  - c) receipt of a live-attenuated vaccine in the four weeks prior to inclusion
- 2) Vaccine refusal
- 3) Indication for an early MMR vaccination, including
  - a) Measles outbreak
  - b) Planned immunosuppression (indication to an accelerated schedule to be completed before starting an immunosuppressive treatment)
  - c) Travel to a region with a high risk of measles outbreak
- 4) Indication for vaccination with MMR-varicella (MMRV) instead of MMR, including
  - a) severe eczema
  - b) parental will
- 5) Parental inability to follow the procedures of the study, e.g. due to language problems, psychological disorders, known/suspected non-compliance, substance abuse, etc.
- 6) Plan to move out of the country or have prolonged absence during the trial
- 7) Other sibling included in the trial
  - a) In the case of multiple pregnancy, only one child can be randomised.
- 8) Any temporary contra-indication to MMR, including child being sick (active significant illness)
  - a) Inclusion can be delayed a few days until the illness resolves

## 7.2 Recruitment and screening

As mentioned in section 2.7, the parents of potential subjects are informed about the trial via pamphlets, email, notice board and/or website/social media in Geneva, Switzerland. The pamphlets include a pitch about the study and a QR code with a link to a website where they can read further information and access the participant informed consent form (PICF), with contact details for further questions. Interested parents are given the opportunity to talk with a member of the research team if they have any questions, and to consult the treating paediatrician prior to enrolment.

Parents of potential subject are then screened by investigators (or designee). If the subject is deemed to be eligible (see section 7.1), the investigators (or designee) explain to the parent the nature of the study, its purpose, the procedures involved, the expected duration, the potential risks and benefits and any discomfort it may entail. The parent of each subject is informed that the participation in the study is voluntary, that they may withdraw their children from the study at any time, and that withdrawal of consent will not affect subsequent medical assistance and treatment. The parent of each subject are informed that they can ask any question, and consult with family members, friends, treating physicians or other experts before deciding about their participation in the study. The parent of each subject is given a subject information sheet and a consent form describing the study and providing sufficient information for the parent to make an informed decision about their child's participation in the study. Enough time is given to the parents of the subjects. The formal consent of the parent of each subject, using the approved consent form, is obtained before the subject is submitted to any investigation procedure.

The parent of each subject should read, understand, and voluntarily agree before signing and dating the informed consent form, and is given a copy of the signed document. The consent form is signed and dated by the subject and the PI (or designee). The signed consent form it is retained as part of the investigation records.

There is no compensation for participating in the trial.

There are no further screening procedures for eligibility, including no test are required.

If enrolment goal are not met, measures will be taken to increase recruitment, such as extension within Geneva or to other location, or hiring supplementary staff.

## 7.3 Assignment to study groups

Once informed consent is signed, consent to blood tests at 6, 9 and 24 months of age will be sought, and will determine whether a child participates in Part 1 only, or both Part 1 and Part 2. For subjects consenting to blood tests, the baseline blood will be collected prior to randomisation. In the eventuality that the blood collection fails, the subject will be considered as not consenting to blood tests (participation to Part 1 only), given that the laboratory analysis in Part 2 cannot be made in the absence of a baseline blood sample.

As described in section 6.2.1, randomisation will be in 4 groups of similar size, using a web-based randomisation procedure, stratified by consent to blood tests (yes/no), in randomly permuted blocks of variable length (4 or 8), enabling to prevent predictability of intervention assignments. The randomisation lists will be generated prior to the initiation of the study by someone not involved in the study analysis and will be integrated into REDCap.

Subjects will be randomised at 6 months of age by an investigator (or designee) using the REDCap platform. Subjects will receive the two MMR vaccines according to their randomisation group (current schedule or modified schedule for the first and the second MMR dose, see section 6).

## 7.4 Criteria for withdrawal / discontinuation of participants

In accordance with the principles of the current revision of the Declaration of Helsinki, a volunteer has the right to withdraw from the study at any time and for any reason, and is not obliged to give his/her reason(s) for doing so. In the present study this right is extended to the subject's parents. The Investigator may also withdraw the subject at any time in the interests of the subject's health and well-being. The DSMB may also recommend withdrawal of volunteers.

In addition, the subject may withdraw/be withdrawn for any of the following reasons:

- Ineligibility, jeopardising the health of the participant
  - either arising during the study or retrospectively, having been overlooked at screening
  - if the ineligibility is discovered after study inclusion, the participant will be withdrawn

from the study only in the event that the factor leading to ineligibility could directly jeopardise the health of the participant if the participant continues in the trial.

- Significant protocol deviation
  - failure to follow protocol procedures that specifically relate to the primary outcome of the study
- Volunteer non-compliance with study requirements
- An AE, which requires discontinuation of the study involvement or results in inability to continue to comply with study procedures

The reason for withdrawal will be recorded in a CRF. If withdrawal is due to an AE, appropriate follow-up visits or medical care will be arranged, with the agreement of the subject's parent, until the AE has resolved, stabilised or a non-trial related causality has been assigned.

It is not planned to replace subject who have withdrawn from the study, should it be less than the maximum 15% allowed in the sample size calculation (see section 11.2).

Any subject who do not complete the questionnaires and fails to attend scheduled follow-up visits with neither communication with the study team nor a clear rationale will be deemed to have withdrawn from the study. If a subject withdraws from the study, clinical data and blood samples collected before his/her withdrawal from the trial will be used/stored unless the subject's parent specifically requests otherwise.

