## **8.5 Data Collection and Follow-up for withdrawn participants**

As stated in section 7.4, If withdrawal is due to an AE, appropriate follow-up visits or medical care will be arranged, with the agreement of the subject's parent, until the AE has resolved, stabilised or a non-trial related causality has been assigned.

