### 9.3.2 Visit 1: Baseline and randomisation, 6 months of age ( $t_0 \pm 2$ weeks)

**Eligibility check** by investigators, with review of past medical history and of vaccination records, re-evaluation of inclusion and exclusion criteria.

**Target clinical examination** will be performed if needed, to ensure that there is no temporary exclusion criteria (e.g. if the child is sick, the inclusion can be delayed a few days until the illness resolves).

**Overview of the trial** by investigators, using the study flow chart and the participant informed consent form. Correct comprehension of the trial will be checked, with the possibility for parents to ask any remaining question.

**Blood collection will be discussed** in further details for interested parents.

**Further information** will be given to all parents, including that

- The treating physician of their child will be contacted to inform about the trial, corroborate their child's medical history and seek additional information.
- Authorised individuals other than their treating physician may examine their child's medical records.
- The blood samples taken as part of the study will be coded and stored for a period of maximum 15 years; this duration has been chosen given the likelihood that progress in the nascent field of non-specific effects of vaccines may benefit substantially from the reanalysis of study samples. Upon the approval of the Sponsor, samples may be sent outside of Switzerland to collaborating research laboratories for non-commercial research purposes.
- There is no compensation for participating in the trial.
- They are free to withdraw at any time. Unless they specifically request complete consent withdrawal, the long-term data collection, including access to medical records, will continue, in order to avoid bias as much as possible.

**Informed consent** will be sought, once the subject's parent confirm understanding and voluntarily agreeing in participating; the parent and the investigator will both date and sign the consent form.

**Inclusion in the trial**, the parent is given a copy of the signed document; the original copy is securely filed in the study documentation.

**Baseline questionnaire** will be filled down by the subject parents and reviewed with the investigator. It includes questions on demographics, medical history, and exposure, as detailed in Table 4 in section 9.2.

**Eczema assessment** will be performed, using *SCORAD* score.

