#### 11.4.1 Datasets to be analysed, analysis populations

The groups will be compared by intention-to-treat analysis. Sensitivity analysis will be done using an as-treated (per-protocol) analysis and will only include participants with available data who received the interventions as planned.

Subgroup analysis are planned (by sex, risk factor, underlying maternal immunity, etc.) and will be detailed in the statistical analysis plan.

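### Section 7.4 permits withdrawal for deviation or non-compliance without requiring outcome collection to continue, which sits badly with section 9.3.2 and the intention-to-treat analysis

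*Protocol*

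**What the plan says.** Protocol section 7.4 lists reasons why a child may withdraw or be withdrawn. Two of them concern adherence rather than safety or consent: a significant protocol deviation, defined as "failure to follow protocol procedures that specifically relate to the primary outcome of the study", and "Volunteer non-compliance with study requirements". The ineligibility item in the same list permits withdrawal only where the child's health could be directly at risk; the two adherence items carry no such limit. A family that neither completes questionnaires nor attends visits, without communication or a clear reason, "will be deemed to have withdrawn from the study".

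On data, 7.4 says that "clinical data and blood samples collected before his/her withdrawal from the trial will be used/stored" unless the parent asks otherwise. Section 8.5, which by its title covers data collection in withdrawn participants, and section 9.2.5 repeat one provision from 7.4: "If withdrawal is due to an AE, appropriate follow-up visits or medical care will be arranged".

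The Visit 1 text in section 9.3.2 gives parents a different rule: "Unless they specifically request complete consent withdrawal, the long-term data collection, including access to medical records, will continue, in order to avoid bias". Section 11.4.1 states: "The groups will be compared by intention-to-treat analysis". It keeps the restriction to children vaccinated as planned for a sensitivity analysis.

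**The concern.** An intention-to-treat comparison needs outcomes on every randomised child, including those who leave the allocated schedule. Sections 7.4, 8.5 and 9.2.5 give staff discretion to withdraw a child for poor adherence and do not tell them to keep collecting that child's outcomes. The one passage that does, and that gives avoidance of bias as its reason, is in the information given to parents at Visit 1.

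The trial is open-label without placebo, and the primary outcome is parent-reported through fortnightly questionnaires. The decision to withdraw is therefore made with the allocation known, and may be related to both allocation and exposure to infection. If follow-up stops at that point, the children left in the main analysis begin to resemble the set that 11.4.1 reserves for sensitivity analysis. A statistical analysis plan can specify how missing outcomes are handled, but it cannot supply outcomes that were not collected.

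**Working it through.** **1. The rules side by side**

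- Section 7.4: adherence is a ground for withdrawal; data from before withdrawal are kept; later data are not mentioned.
- Sections 8.5 and 9.2.5: follow-up after withdrawal is described only where an adverse event was the reason.
- Section 9.3.2: collection, including medical records, continues unless consent is completely withdrawn.
- Section 11.4.1: intention-to-treat is the main comparison.

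Staff working from the first two could stop collection where the third says it goes on and the fourth needs it.

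**2. The plan's own sample size**

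Inputs from section 11.2: control rate 0.29 per month, SD 0.32, 30% reduction, two-sided 0.05, 80% power, 85% completion.

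- Difference: δ = 0.29 × 0.30 = 0.087 per month.
- Evaluable per arm: n = 2 × (1.960 + 0.842)² × 0.32² / 0.087², which rounds up to 213.
- Randomised per arm: 213 / 0.85, which rounds up to 251, so 502 in total against the stated 500. The stated figure reproduces.

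**3. Power by completion**

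Power = Φ(δ / (0.32 × √(2/n)) − 1.960), with n = 250 × completion:

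| Completion | n per arm | Power |
|---|---|---|
| 100% | 250 | 86.0% |
| 92.5% | 231.25 | 83.2% |
| 85% | 212.5 | 80.0% |
| 80% | 200 | 77.6% |

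There is no margin at 85%. Section 7.4 counts withdrawals against the same 15% allowance. If half of a 15% loss were recovered by continued collection (an assumption), completion would be 92.5%.

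**4. Illustration of bias**

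The documents give no withdrawal rate by arm and no infection rate in withdrawn children, so every input here is an assumption:

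- there is no true effect;
- a fraction f of the early-MMR arm is withdrawn and none of the control arm;
- all primary-outcome data of those children are lost;
- their infection rate is r times that of compliers.

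The early arm is then left with compliers only (relative rate 1), while the control arm keeps its full mix. Apparent IRR = 1 / ((1 − f) + f × r).

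| f | r = 0.5 | r = 2 |
|---|---|---|
| 2% | 1.01 | 0.98 |
| 5% | 1 / 0.975 = 1.03 | 1 / 1.05 = 0.95 |
| 10% | 1 / 0.95 = 1.05 | 1 / 1.10 = 0.91 |
| 15% | 1 / 0.925 = 1.08 | 1 / 1.15 = 0.87 |

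If the control arm were the one affected, the ratios would invert; at 10% withdrawn they would run from 0.95 to 1.10. The planned effect is an IRR of 0.70.

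**The case against.** The passages can be read together. Section 7.4 governs data already in hand and section 9.3.2 governs later data, and nothing in 7.4 forbids further collection. A reader might infer that 7.4 confines the analysis to earlier data and flatly contradicts Visit 1. The text does not go that far: the restriction is inferred from silence in 7.4 and from the adverse-event wording in 8.5 and 9.2.5. The Visit 1 sentence is also addressed to parents who withdraw, so for a child withdrawn by the investigator the conflict is by implication.

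A reader might also infer that intention-to-treat is broken by exclusions specific to each arm, such as a missed 6-month dose or an MMR before 9 months. That is one reading. Procedures relating to the primary outcome could equally mean the questionnaires. Section 3.7 allows MMR in an outbreak without mentioning withdrawal, and because the 6-month dose is given at the randomisation visit, missed doses should be uncommon. Withdrawal is permitted, not required. Earlier data stay usable, and section 11.5 lists missing-data methods. Deemed withdrawal requires missed questionnaires and missed visits without contact, which is closer to loss to follow-up than to removal of poor responders.

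Nor do the documents support treating the bias as a spurious benefit, or as beyond repair. The direction depends on who is withdrawn, and paediatrician contact and medical records could recover some episodes.

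These points limit the claim but do not remove it. Adherence remains a discretionary ground for withdrawal, and the sections that staff would consult contain no instruction to keep collecting outcomes.

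**Conclusion.** The point holds as an internal inconsistency and a weakness in the withdrawal rule. Used as written, 7.4 with 8.5 and 9.2.5 can lose outcomes that the intention-to-treat comparison needs, which undermines that comparison without making it impossible.

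Size and direction are unknown. The illustrated distortion is modest beside the planned 30% reduction and can go either way. It overstates the effect of withdrawal wherever earlier data are retained or both arms lose children alike. The power calculation is firmer because it uses the plan's own inputs: each loss beyond 15% takes power below 80%. The matter should be settled in the protocol, since follow-up after withdrawal is fixed there.

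**What to change.** - In 7.4, remove protocol deviation and non-compliance as grounds for ending data collection.
- Define two separate states: no longer following the allocated schedule, where outcome collection continues as planned for every child; and consent to data collection withdrawn, where it stops.
- Treat children whose families stop responding as having missing data, with paediatrician contact and record checks continuing as far as consent allows.
- Carry the rule in 9.3.2 into 7.4, 8.5 and 9.2.5, and state that it also applies when the investigator makes the decision.

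Decisions taken for a child's safety are outside this change, and the sample size stays at 500. The cost is a wording amendment and some continued follow-up effort for the children concerned. The questionnaires, paediatrician contacts and record checks are already in the schedule for every child (sections 9.1 and 9.2), although section 14.1 allows follow-up to be shortened if funding falls short.
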